13.2 STUDY RECORDS RETENTION

Source data is retained at the clinical sites until completion of the trial and then will be stored for a period of time as specified by the Sponsor's quality system.

13.3 PROTOCOL DEVIATIONS

An Investigator is required to conduct this study in accordance with the signed Investigator's Agreement, this investigational plan, applicable laws and applicable national regulations, and any conditions of approval imposed by the reviewing IRB or Ethics Committee and regulatory agency (e.g.: FDA or Competent Authority).

Protocol deviations are a fact of life with any clinical trial. Deviations may be anticipated (e.g.: known delay in a follow up visit), inadvertent (e.g.: unplanned delay or miss of a follow up visit due to a family emergency), or unanticipated on an emergency basis (e.g.: trauma may require device removal to accommodate contraindicated procedures). Except in emergency situations, protocol deviations requires prior Sponsor approval; and if the deviation may affect the scientific soundness of the plan or the rights, safety, or welfare of subjects, prior IRB or Ethics Committee approval is required. An Investigator shall notify the Sponsor and the reviewing IRB or Ethics Committee of any deviation from the investigational plan to protect the life or physical well-being of a subject in an emergency. Such notice shall be given as soon as possible, but no later than five working days after the emergency occurred. All deviations from the investigational plan must be reported to the Sponsor together with the reason for the deviation and possible corrective actions for the deviations. In some circumstances, the center may be required to notify the center's IRB or Ethics Committee, and the Sponsor will notify the appropriate regulatory agencies.

13.4 PUBLICATION AND DATA SHARING POLICY

Publications addressing the Early Bird Study results will be managed by a publications committee. MicroOptx will form the Early Bird Study publications committee to include members of MicroOptx and participating Investigators. The committee shall elect its chair at the first publications meeting, which will be held near the time of study start. Each participating institution may provide one representative to the publications committee. Additional members may be added based on approval of the committee. The committee will develop a publication strategy that will include a final publication plan. The scientific validity and timing of publications will be evaluated in order to maximize the benefits derived from the publication of the world wide clinical data of the Early Bird Study. All publications and strategy will be reviewed and approved by the Publications Committee. In general, publications utilizing study data will be managed as follows:

Authorship Selection

Authors will be selected based on the following criteria:

- The quantity of patients who are enrolled in the study, provided that quality compliant data is collected (i.e., data that is complete, accurate and received within a reasonable time frame)
- Documented Investigators' participation in the study development process
- The quality and quantity of prior publication history in general and with MicroOptx Clinical Research
- At least one MicroOptx author providing substantive contribution to the study shall be considered

Confidentiality

The Committee, MicroOptx, and all Investigators and authors will ensure that no information which would reveal a patient's identity is used in any publication. Information which could be used to establish a patient's identity, should not be provided to MicroOptx. Authors and MicroOptx will take every reasonable precaution to protect the identity of patients enrolled in the trial.

Review and Communication Guidelines

[figure not shown]
Investigators will receive a communication regarding the authorship selection, the publication coauthors, and to which scientific platform the publication will be submitted.

APPENDIX

MicroOptx[®]

Statistical Analysis Plan for the US Early Bird Study (Protocol 6054 – formerly 4039) NCT03469297

29 Jul 2022

Version 2.0

Approved by:

[name], Clinical Research

29 Jul 2022

Date

1. Introduction

This document outlines intended analyses to characterize the early feasibility of the Beacon Aqueous MicroShunt, Model 2D, in support of a future IDE submission.

In order to provide a comprehensive assessment, data will generally be summarized for all implanted subjects. Due to sample size constraints, no formal statistical hypothesis tests will be specified; however, statistical significance may be assessed in exploratory fashion.

An enrollment flow diagram will summarize the number of subjects who were consented, implanted, screen failed (with reason), withdrawn prematurely (with reason), and study completers.

2. Baseline Demographics and Medical History

Key baseline demographic and medical history variables will be summarized for all consented and implanted subjects. Continuous measures will be summarized using N, mean, standard deviation, median, and range. Categorical measures will be summarized using frequency distributions.

Table X. Summary of I	raphic Characteristics	
	N	Mean ± SD (Median) Min, Max
	or	or
Baseline Characteristic	n/N	%
Age (years)	#	##.#
Gender		
Female	#/#	##.#
Male	#/#	##.#
Ethnicity		
Hispanic or Latino		
Not Hispanic or Latino		
Race		
White or Caucasian		
Black or African American		
Asian		
American Indian or Alaska Native		
Hawaiian or Other Pacific Islander		
Other		
Declined to Answer		

Table X. Summary of Demographic Characteristics					
Baseline Characteristic	N or n/N	Mean ± SD (Median) Min, Max or %			
Level of Education Did Not Complete High School High School Attended College Undergraduate Degree Attended Graduate School Graduate Degree Other					
Eye Color Brown Blue Green Hazel Implanted Eye					
OD – Right OS – Left					

Table X. Summary of Medical & Ophthalmic History					
Diagnosis/Procedure	N or n/N	Mean ± SD (Median) Min, Max or %			
General Medical History					
Hypertension	#/#	##.#			
Diabetes	#/#	##.#			
Gout					
Etc					
Ophthalmic History					
Open Angle Glaucoma					
Dry Eye					
Cataract					
Etc					
Ophthalmic Surgical History					
Phacoemulsification					
Selective Laser Trabeculotomy					
Etc					

3. Effectiveness

3.1 Primary Effectiveness

The primary effectiveness parameter includes the following measure in the implanted eye:

• Overall responder rate, with responder defined as achieving at least 20% reduction from baseline in diurnal IOP

3.2 Secondary Effectiveness

Secondary effectiveness parameters of interest in the implanted eye include:

- Mean change from baseline in diurnal IOP
 - o Standard deviation, median, range, and sample size at each visit
 - o Mean percent reduction, along with median and range, at each visit
- Responder rate, with responder defined as achieving follow-up diurnal IOP less than or equal to 14 mmHg
- Proportion of participants with at least 20% reduction in IOP on the same or fewer IOP-lowering medications
- Change in IOP-lowering medications
 - Mean number of IOP-lowering medications in the implanted eye at each visit and corresponding standard deviation at each visit
 - Overall mean percent reduction at each visit
 - \circ Total number of medications per patient (N/%)
 - O Shift table at each visit (decreased, no change, increased)

3.3 Exploratory Effectiveness

Exploratory effectiveness parameters of interest in the implanted and contralateral eye include:

- Changes from baseline in the Schirmer Tear Test
 - o Mean and standard deviation in the implanted eye at each visit
 - O Shift tables at 6-, 12-, and 24-months according to:
 - 0-5mm: severe
 - >5-10mm: moderate
 - >10-15mm: mild
 - >15: normal

- Treatment satisfaction questionnaire (TSQ)
- Glaucoma progression
 - o Summary of changes in visual field in the implanted eye over time
 - o Cup/disc ratio in the implanted eye over time

4. Safety Assessment

4.1 All AEs and SAEs

The primary summary of safety will consist of all adverse events (AEs), adverse device effects (ADEs), serious adverse events (SAEs), and unanticipated adverse device effects (UADEs) occurring in the implanted eye through 6 months post-implant, by type, summarized by study and overall. For each reported event, the number of events (# Event), number of participants with an event (n), and the percentage of participants among the total sample size (N) will be summarized. Supportive analyses will include summaries of device-related adverse events and secondary surgical interventions through 24 months of follow-up.

Table X. Summary of Adverse Events								
Event	# Events	% (n/N) Participants						
Adverse Events								
Serious Adverse Events								
Device-Related Adverse Events Possibly Probably Definitely Procedure-Related Adverse Events Possibly Probably Definitely								
Study Device and/or Procedure Related Adverse Events								
Serious Study Device and/or Procedure Related Adverse Events								

Table X. Summary of Device-Related Adverse Events					
Participant ID (AE#)	Description of Event	# Events	% (n/N) Participants		

Table X. Summary of Secondary Surgical Interventions						
Participant ID (AE#)	Surgical Intervention	# Events	% (n/N) Participants			

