5 STUDY ENROLLMENT AND WITHDRAWAL

5.1 PARTICIPANT INCLUSION CRITERIA

Inclusion Criteria

- 1. Age 22 years and older.
- 2. Best corrected visual acuity of 20/400 or worse in the study eye.
- 3. Fellow eye with visually acuity of 20/200 or better and the visual field no worse than study eye. If the study eye has no light perception, the fellow eye may have no light perception or better.
- 4. Intraocular pressure in the study eye greater than or equal to 21 mm Hg and less than or equal to 50mm Hg.
- 5. Primary open-angle glaucoma (confirmed by gonioscopy).
- 6. Glaucomatous optic nerve damage as evidenced by any of the following optic disc or retinal nerve fiber layer structural abnormalities:
 - (1) Diffuse thinning, focal narrowing, or notching of the optic disc rim, especially at the inferior or superior poles with or without disc hemorrhage;
 - (2) Localized abnormalities of the peripapillary retinal nerve fiber layer, especially at the inferior or superior poles; or
 - (3) Optic disc neural rim asymmetry of the two eyes consistent with loss of neural tissue
- 7. Humphrey Visual Field (HVF) demonstrating visual field defects consistent with glaucomatous optic nerve damage:

For moderate glaucomatous loss

- Mean deviation > 6dB < -12 dB
- Fewer than 37 points depressed below the 5% probability level and fewer than 20 points below the p<1% level
- No absolute deficit in the central 5 degrees
- Only one hemifield with sensitivity of < 15 dB in the 5 central degrees

For advanced Glaucomatous loss

- Mean deviation > -12 dB
- More than 37 points depressed below the 5% probability level and more than 20 points below the p<1% level
- Absolute deficit in the central 5 degrees
- Sensitivity < 15 dB in the 5 central degrees in both hemifields

in

- 8. At least two contiguous clock hours of intact conjunctiva near the limbus between clock hours of 9:00 and 03:00 in the study eye.
- 9. Adequate space in the anterior chamber of the study eye sufficient to support implant with the BGI, defined as two contiguous clock hours of scleral spur visualization via gonioscopy, without compression, in the superior 180 degrees of the anterior angle.
- 10. Able and willing to comply with protocol requirements.
- 11. Able to understand and sign the Informed Consent form.

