7.1.3.16 LENS STATUS FOR PHAKIC EYES

The lens status for phakic eyes will be described for both the test and contralateral eye if applicable.

A modified LOCS III grading system utilizing a 0-5 single digit scoring system will be used to evaluate all eyes for lens changes and to evaluate those changes over time. Standardized definitions in this instrument will be used to determine "change".

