8.1.6 PRE-SPECIFIED LIST OF ADVERSE EVENTS

Adverse events listed below are provided on the case report form along with a method for recording other adverse events not listed, based on the recognized standard ANSI Z80.27-2014.⁷

- Corneal edema
- Progression of cataract requiring cataract extraction

- Wound leak
- Suture abscess or other local infection
- Endophthalmitis
- Chronic iritis
- Hyphema
- Strabismus
- Macular edema
- Vitreous hemorrhage
- Suprachoroidal hemorrhage
- Retinal detachment
- Device malfunction
- Device blockage not requiring surgical revision
- Device blockage requiring surgical revision
- Implant migration (of any kind) not requiring surgical intervention
- Implant migration requiring surgical revision
- Implant exposure or extrusion
- Flat anterior chamber requiring anterior chamber reformation
- Hypotony (e.g., IOP <6 mmHG and associated with concomitant hypotonous findings are noted, including: Corneal edema/folds, shallow anterior chamber, hypotonous maculopathy, significant choroidal detachments or effusion)
- Hypotony maculopathy
- Choroidal effusion requiring surgical drainage
- Substantial increase in IOP vs. baseline (defined as >10 mmHg)
- Substantial visual field loss vs. baseline (e.g., 10 db loss)
- Substantial visual acuity loss vs. baseline (e.g. 10 or more ETDRS letters)
- Event requiring unplanned ocular surgical re-intervention

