10.5 SAMPLE SIZE

This trial is a first-in-human feasibility trial of the Brown Glaucoma Implant. No formal tests of hypothesis are planned, and so sample size is not statistically derived. A total of ten enrolled and implanted subjects are believed to be sufficient to confirm preclinical findings, provide evidence of feasibility of efficacy, and determine whether or not the observed safety profile justifies further study.

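### SAP 4.1 divides every adverse event by the total sample, which may understate cataract and acuity-loss risk in the eyes that can have those events

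*SAP*

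**What the plan says.** SAP 4.1 covers events in the implanted eye through 6 months. For each reported event it gives the number of events, the number of participants affected, and a percentage: "the percentage of participants among the total sample size (N) will be summarized". The table shells in that section repeat the n/N format. The population behind N comes from SAP section 1, where "data will generally be summarized for all implanted subjects". Protocol 10.5 sets the planned number: "A total of ten enrolled and implanted subjects are believed to be sufficient", and notes that "sample size is not statistically derived".

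Two events on the pre-specified list in protocol 8.1.6 matter here:

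- Lens: "Progression of cataract requiring cataract extraction".
- Acuity: "Substantial visual acuity loss vs. baseline (e.g. 10 or more ETDRS letters", in the protocol's own example.

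Eligibility lets in eyes that cannot have one or the other.

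- Inclusion criterion 3 (protocol 5.1) plainly foresees blind study eyes: "If the study eye has no light perception, the fellow eye may have no light perception or better". Criterion 2 requires 20/400 or worse and sets no lower bound.
- Neither protocol 5.1 nor 5.2 has a criterion on lens status. Protocol 7.1.3.16 allows for eyes without a natural lens: "The lens status for phakic eyes will be described for both the test and contralateral eye if applicable". The surgical-history shell in SAP section 2 has phacoemulsification as an example row.

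**The concern.** A pseudophakic eye has no natural lens in which a cataract could progress. An eye without light perception has no acuity to lose, and an eye reading fewer than 10 letters at baseline cannot lose 10. Under SAP 4.1 such eyes count as event-free for harms they could not have had, whatever the device does. This is separate from missing follow-up, because it applies from the day of implant to subjects with complete data.

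Protocol 2.3.1 names cataract formation or progression and permanent vision loss as potential risks of the device. Protocol section 3 asks whether the safety profile justifies further study, and SAP section 1 says the analyses support a later IDE submission. For that purpose a reader will want to know the risk in an eye that still has a lens or some measurable vision, and the planned percentage does not give it.

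**Working it through.** **Inputs.** N = 10 (protocol 10.5). The denominator is N for every event type (SAP 4.1). The number of implanted eyes not at risk, k, is not in the documents. It is therefore an assumption, shown as a range, and it need not be the same for lens and acuity events. The documents give no expected event rate and no percentage of their own to reproduce.

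**Step 1: relation between the two rates.** Let m = N − k be the eyes at risk and n the participants with the event. Then

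n/N = (n/m) × (m/N), so n/m = (n/N) × (N/m).

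Since m cannot exceed N, the reported percentage equals the at-risk percentage or lies below it; it is never higher.

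**Step 2: one event, N = 10.** The planned table would show 1/10 = 10.0% in every row below. Intervals are two-sided 95% Clopper-Pearson; on 10 eyes, one event gives 0.3 to 44.5%.

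| k (assumed) | m | at-risk rate n/m | exact 95% CI | factor N/m |
|---|---|---|---|---|
| 0 | 10 | 1/10 = 10.0% | 0.3 to 44.5% | 1.00 |
| 2 | 8 | 1/8 = 12.5% | 0.3 to 52.7% | 1.25 |
| 3 | 7 | 1/7 = 14.3% | 0.4 to 57.9% | 1.43 |
| 5 | 5 | 1/5 = 20.0% | 0.5 to 71.6% | 2.00 |

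**Step 3: no events.** Both rates are 0%, so nothing is understated. What changes is the evidence behind the zero. The exact upper limit is 1 − 0.025^(1/m):

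- m = 10: 30.8%
- m = 8: 36.9%
- m = 7: 41.0%
- m = 5: 52.2%

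**Step 4: chance of seeing the harm at all.** Assume, for illustration only, a true risk of 20% in eyes at risk. The chance of at least one event is 1 − 0.8^m: 89% with 10 eyes at risk, 79% with 7 and 67% with 5. The expected value of n/N is 0.20 × m/10: 20%, 14% and 10%.

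**Step 5: which eyes are at risk of the acuity event.** Removing only eyes without light perception is not enough when the event is a loss of 10 letters. An eye with a baseline score of 0 to 9 letters cannot meet that definition either, and entry at 20/400 or worse makes such eyes possible. The at-risk set for this event is eyes scoring at least 10 letters at baseline.

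**The case against.** **The percentage is not wrong.** It is a correctly labelled share of all implanted subjects, with n and N both printed, in a descriptive study without hypothesis tests. This stands. What is missing is a second denominator; there is no arithmetic error.

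**Understatement is not shown.** A reader might infer that the lens and vision harm rates are definitely too low. The documents do not support that. It needs at least one eye not at risk and at least one event, and neither count is given. An example row for phacoemulsification in a table shell says nothing about frequency. This also stands, and the factor starts at 1.00.

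**No limits are planned.** SAP 4.1 plans no confidence intervals for adverse events, and an event type with no occurrences may not get a row. So the upper limits above do not correct a planned output; they show what a bare zero would leave unsaid.

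**No rule depends on these rates.** The halting rule in protocol 8.7 counts subjects with serious device- or procedure-related events, and no threshold is set on a cataract or acuity percentage. True, and it limits the importance of the point.

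**The listings already answer it.** SAP section 6 plans a line listing of adverse events and a summary for each participant, and protocol 10.4.9 adds listings by subject. With about ten subjects, much of the at-risk count could be rebuilt. This stands only in part. An adverse event listing need not show lens status or baseline acuity for subjects without events, who make up most of the denominator. The content of the participant summaries is not specified, and the history table is aggregate.

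**Conclusion.** The point holds in a conditional form. SAP 4.1 fixes one denominator for all events, while the eligibility criteria admit eyes that cannot have two of the pre-specified harms. The reported percentage may therefore understate the risk in eyes with a lens or measurable sight, and it cannot overstate it. With N = 10 the factor runs from 1.00 (no eyes excluded) through 1.25 and 1.43 to 2.00 (five excluded). When no event occurs, only the strength of the evidence changes. These sizes rest on assumed values of k and on ten implanted subjects. This is an inexpensive improvement in reporting and does not invalidate the safety summary.

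**What to change.** In SAP 4.1, keep n/N for every event and add n/m beside it for two event types. Print m and an exact 95% confidence interval, including when n = 0. Suggested text:

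- For cataract or other lens events, m is the number of implanted eyes that were phakic at baseline.
- For acuity loss defined as 10 or more ETDRS letters, m is the number of implanted eyes with a baseline score of at least 10 letters.
- If a drop in acuity category is also counted as an event, m for that event is the number of implanted eyes with better than no light perception at baseline.

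No new data are needed. Protocol 7.2.1 and Table 3 already schedule ETDRS acuity and lens status at baseline, and the logMAR formula in protocol 7.1.3.1 uses the number of letters read. The cost is a few lines of SAP text and one added column for two event types. The downside is that these two rates become less favourable and less precise.

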4.2 Implant Procedure Characteristics

Key implant characteristics will be summarized for each participant. MicroOptx Chief Scientific Officer reviewed all available implant videos to determine if the device implants were corneal or scleral in location.

- Insertion angle (anterior, medial, or posterior)
- Implant position (clock hour)
- Implant location (corneal or scleral)
- Ease of implant (easy, moderate difficulty, difficult)
- Explant (yes, no)
- Re-Implant (yes, no)

Table X. Implant Characteristics by Subject							
Subject ID Insertion Implant Implant Ease of Explant Re-Implant Location Implant							

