6.1.3 PRODUCT STORAGE AND STABILITY

6.1.4 IMPLANT PROCEDURE

The Brown Glaucoma implant is intended for single use. It is supplied sterile and individually.

All physicians implanting the MicroOptx Brown Glaucoma Implant must be MicroOptx approved Investigators and implanters in a MicroOptx clinical trial, and have previously completed required didactic and simulated implant training in animals or cadavers. In addition, the first three patient implants of the MicroOptx Brown Glaucoma Implant must be performed with the assistance of a MicroOptx surgical proctor.

To implant the Brown glaucoma Implant:

Surgical Field Preparation

All procedures will be performed using aseptic technique.

[figure not shown]
The affected eye will be individually prepped with a lid/lash scrub using 5% povidone-iodine solution.

[figure not shown]
The gowned and gloved surgeons/techs will then drape the eye with a self-adhesive ophthalmic aperture drape such as the 3M ophthalmic "Steri-Drape".

An operating microscope with photographic or digital imaging required for the implantation procedure is positioned over the eye.

Test Device Implant Procedure

Pre-implant photomicrographs of the eye will be collected. Topical ophthalmic drops of ofloxacin or vigamox, ketorolac and prednisolone will be given three times in the interval between sedation and commencement of surgery. A lid speculum is placed to open the ocular field.

The final implant position of the BGI should be visualized microscopically and verified by gonioscopy. The angle of insertion is recorded on the implantation case report form. Photographs of the implant will be taken to document positioning and location.

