10.4.7 ADDITIONAL SUB-GROUP ANALYSES

Due to the small (n=10) sample size, formal sub-group analyses are not possible or planned.

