4.3 Additional Analyses

Signs of inflammation may indicate insufficient healing of the device within the incisional tract, allowing for micromotion of the implant and increase the risk for adverse events, including endophthalmitis. These signs of inflammation include neovascularization around the implant site, conjunctival hyperplasia (mild, moderate and marked), and partial or complete device extrusion.

Analyses will be conducted to determine whether the implant procedure characteristics described in Section 3.3 contribute to increased inflammation, and whether or not the sign of inflammation was elevated to an adverse event. Further, analyses will be performed to determine the association of inflammation with the outcomes of serious adverse events, device occlusion, and explant.

Analyses will also be conducted to determine whether different anti-inflammatory regimens for inflammation have a differential impact on subsequent adverse events, IOP, diminished flow and device useful life.

5. Subgroup Analyses

Key endpoint data (SAE, SAE or explant, IOP) may be assessed according to pre-defined subgroups. These subgroups include:

- Sex (male, female)
- Race (African American, Caucasian, other)
- Implant location (scleral, corneal)
- Allergies with ocular involvement

Other subgroups may be identified in the course of analysis and will be assessed in a *post hoc* fashion.

6. Other Information

In addition to the described data analysis, the following information will also be presented as part of the safety assessment:

- Updated endothelial cell loss (ECL) analysis
- Individual Participant Summaries for each participant
- Line listing of all adverse events
- Line listing of all protocol deviations

Subject # (Eye)	BL ECC	3 mo ECC	6 mo ECC	12 mo ECC	24 mo ECC	3 mo ECC Δ** (%Δ^^)	6 moECC Δ (%Δ)	12 mo ECC Δ (%Δ)	24 mo ECC Δ (%Δ)
##-## (OD)	####	####	####	####	####	+## (#.#)	+## (#.#)	+## (#.#)	+## (#.#)
##-## (OS)	####	####	####	####	####	+## (#.#)	+## (#.#)	+## (#.#)	+## (#.#)

^{*} ND = Not Done

 $^{^{\}wedge}$ NA = Not Applicable

^{**} A positive value indicates higher endothelial cell count relative to baseline reading, while a negative value indicates a loss in endothelial cells (ECL) since baseline

 $^{^{\}wedge \wedge}$ % Δ = (Follow-Up Visit ECC- Baseline ECC)/Baseline ECC * 100

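### Corneal or scleral location was read from videos by a sponsor officer before the SAP was signed, with no stated criteria or masking, and the protocol does not support calling it a pre-defined subgroup

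*SAP*

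**What the plan says.** SAP 4.2 (Implant Procedure Characteristics) lists implant location, corneal or scleral, among the items summarised for each participant. It says that an officer of the sponsor "reviewed all available implant videos to determine if the device implants were corneal or scleral in location". The verb is in the past tense, so the reading came before the SAP of 29 July 2022. The SAP does not say what makes an implant corneal or scleral, whether the reader was masked to outcomes, whether anyone else read the videos, how many eyes had a video, or what happens to an eye without one.

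Location is then used twice:

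- SAP 5 (Subgroup Analyses): "Key endpoint data (SAE, SAE or explant, IOP) may be assessed according to pre-defined subgroups". Scleral versus corneal location is one of the four subgroups listed. The sentence after the list keeps the term post hoc for subgroups that emerge during analysis.
- SAP 4.3 (Additional Analyses): analyses are to examine whether the implant procedure characteristics contribute to inflammation. Here the SAP commits to the analysis rather than leaving it optional.

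Protocol 10.4.7 says that, because of the sample size, "formal sub-group analyses are not possible or planned". Protocol 7.2.2 gives implant location only as left or right eye. Protocol 6.1.4 has the insertion angle recorded on the implantation form and adds: "Photographs of the implant will be taken to document positioning and location".

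**The concern.** A subgroup label is useful when it is fixed without regard to how each eye fared. Here a person inside the sponsor sorted the eyes in an unmasked study, and the SAP describes no safeguard. If a borderline placement is read with knowledge that the eye was explanted or had a serious event, the reading can produce an apparent location effect. A by-subject listing shows which label each eye received, but not how it was chosen.

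The word pre-defined adds to the problem. The SAP contrasts it with post hoc, so a reader will take a location result as planned in advance. The SAP's stated purpose is to back a later IDE submission, and SAP 1 allows significance to be assessed in an exploratory way. A location difference could therefore be presented there with a p-value and more standing than its origin justifies.

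**Working it through.** **1. Was location defined in advance?** The passages side by side:

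| Source | Content |
|---|---|
| Protocol 7.2.2 (version of 27 January 2019) | Implant location means left or right eye |
| Protocol 6.1.4 | Insertion angle on the form; photographs taken; no corneal/scleral item |
| Protocol 10.4.7 | No formal subgroup analyses |
| Protocol 10.1 | No formal SAP to be written |
| SAP 4.2 and 5 (29 July 2022) | Corneal/scleral variable appears, already read; subgroup called pre-defined |

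Between the two documents lie about three and a half years. In the documents supplied, the variable and the subgroup first appear in the SAP.

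**2. Could outcomes have been known to the sponsor?** Protocol 10.6.1 has no masking. Protocol 8.7 has the sponsor review safety data every two months. Protocol 10.4.6.2 has effectiveness assessed informally and periodically. Expected accrual was one to three months (Protocol 1). SAP 6 lists an "Updated endothelial cell loss (ECL) analysis", which suggests an earlier look at cell counts. The sponsor thus had planned and repeated access to outcomes. None of these passages dates the video reading or says what the reader knew.

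**3. How much can one eye matter?** There is no plan figure to reproduce. Protocol 10.5 gives ten subjects and says the number is not statistically derived. The SAP names no test or threshold for subgroups. The event counts, the splits, the Fisher exact test and the 0.05 benchmark below are therefore assumptions.

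Take 10 eyes with 3 events. If one group has n₁ eyes, the probability of a events in it is C(n₁, a) × C(10 − n₁, 3 − a) / C(10, 3), with C(10, 3) = 120. The two-sided p sums every outcome no more probable than the one observed.

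- 5:5 split, 0 to 3 events in the first group: 10, 50, 50, 10 out of 120.
- 4:6 split: 20, 60, 36, 4 out of 120.
- 6:4 split: 4, 36, 60, 20 out of 120.

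| Table | Difference | Two-sided p |
|---|---|---|
| Start: 3/5 v 0/5 | 60 points | (10 + 10)/120 = 0.167 |
| Event-free eye moves from first to second group: 3/4 v 0/6 | 75 points | 4/120 = 0.033 |
| Event eye moves from first to second group: 2/4 v 1/6 | 50.0 − 16.7 = 33 points | (36 + 20 + 4)/120 = 0.50 |
| Event-free eye moves from second to first group: 3/6 v 0/4 | 50 points | (20 + 4)/120 = 0.20 |

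Other starting points behave in the same way. 4/5 v 1/5 (p = 0.206) becomes 4/4 v 1/6 (p = 0.048) or 3/4 v 2/6 (p = 0.524). 4/5 v 0/5 (p = 0.048) becomes 3/4 v 1/6 (p = 0.190).

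All tables of 10 eyes with splits from 2:8 to 8:2 were also enumerated. Thirty have p < 0.05. In 24 of these, moving a single eye can bring p to 0.05 or above. The six that survive any single move are complete separations at 4:6, 5:5 or 6:4.

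**The case against.** The strongest reply is that this is an optional, descriptive look in a ten-subject feasibility study. SAP 1 specifies no formal tests, and SAP 5 says only that subgroups may be assessed. The protocol rules out formal subgroup analyses, so the SAP does not contradict it. Pre-defined can mean simply named in the SAP. Location is fixed at surgery. The fragility to one eye applies equally to sex, race or allergy in a sample this small. SAP 4.2 lists location, explant and re-implant for each subject, and SAP 6 adds participant summaries and adverse event listings, so a reader can test the influence of any eye.

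Much of this stands, and it limits the severity. It does not answer two things. Sex and race need no judgement from someone who may know the outcome, whereas corneal versus scleral does. And SAP 4.3 commits to using the implant characteristics, so the variable is not wholly optional.

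Two stronger readings are tempting and are not supported. A reader might infer from the past tense and the updated cell-loss analysis that the officer knew the outcomes when classifying. The past tense shows only that the reading preceded the SAP, and cell loss is not one of the named subgroup endpoints. A reader might also infer that some eyes have no video. The phrase about availability is compatible with every eye having one, and Protocol 6.1.4 requires photographic or digital imaging at the procedure.

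**Conclusion.** The point holds in a limited form. The SAP does not describe how location was classified well enough to exclude outcome-aware reading, and the pre-defined label is not supported relative to the supplied protocol. Actual bias is not shown.

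The size is illustrative. With about 10 eyes, one reclassified eye can move an assumed p of 0.17 to 0.033 or to 0.50, and the difference from 60 points to 75 or 33. No decision rule hangs on 0.05; the figures show instability only.

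The assumptions are the planned ten eyes, the invented splits and event counts, and the protocol as supplied (version 9.0, number 4039). The SAP cites protocol 6054 as its successor number. If a later version defined the variable before outcomes were known, the objection to the label would fall away, but the missing criteria and masking would remain. Severity is minor to moderate.

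**What to change.** 1. In SAP 5, describe implant location as post hoc, defined after data collection began.
2. In SAP 4.2, write down the criteria for corneal and scleral, who read the videos and when, what the reader knew of outcomes, and how many eyes had a video.
3. Re-read the existing videos, and the implant photographs where they allow the distinction, against those criteria. Remove IDs and shuffle the order, and link to outcomes only afterwards. Use a current team member not involved in outcome review if there is one. Otherwise use the same reader and state that masking is only partly restored, since someone who has already classified about ten cases may recognise them.
4. Show any eye without usable images as *not classified*.
5. Report location results under both readings, and with each doubtful eye reassigned in turn.
6. Correct the cross-reference in SAP 4.3: it points to Section 3.3, but the implant characteristics are in 4.2.

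The cost is an estimated few hours, with no new data and no added staff. The downside is that location loses its pre-defined label.
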